**Figure 2 Study Schematic Should Dose Prime Be Explored**

DL = Dose Level

\* In-patient observation applies to all cohorts

\*\* Dose level 1 will be higher than Dose Prime

\*\*\* Dose level 2 will be higher than Dose Level 1

*For cohorts instituting a Dose Prime, there will be a 72 hour observation period between the first dose administered to each of the initial patients enrolled (ie, patients contributing to initial DLT evaluation) at a new dose level. In addition to in-patient observation following the C1D1 dose, patients enrolled in cohorts instituting a Dose Prime must also undergo in-patient observation for at least 24 hours (for cohorts where PF-06671008 will be administered IV) or 48 hours (for cohorts where PF-06671008 will be administered SC) following the C1D8 dose.*

### 2.2.3. Criteria for Dose Escalation

*The study has been designed to establish the MTD defined as the dose that yields approximately 27.5% probability of DLT and considers equivalent doses that yield probability of DLT in the interval (Equivalence Interval) 22.5% to 32.5%.*

*Typically patients will be enrolled in cohorts of 2 to 4, but patients could be initially enrolled in cohorts of 1-2 for the lower doses (see section [Dose Escalation Phase \(Part 1\)](#)). The initial 2-4 patients to be included in a cohort will be open to any of the tumor types outlined in the protocol. When required to expand a cohort for further evaluation of the MTD, enrollment of patients may be limited to those with NSCLC, SCCHN, CRC or TNBC.*

*For IV administration cohorts, initial dose levels are provided in [Table 1](#) and will be followed if no DLTs are observed; intermediate doses may be evaluated based on clinical findings. Subsequent maximum dose increases will be a maximum of 2-fold (100%) if no DLTs are observed. For SC administration cohorts, during the initial dose escalation levels, maximum dose increases will be up to 3-fold if no DLTs or safety events that are approaching the limit of tolerability are observed. The initial dose to be evaluated for SC administration will be equal to the dose level selected as the IV Dose Prime. The evaluation of the IV and SC routes of administration will proceed through dose escalation independently according to the mTPI method. Once the first DLT is observed, the maximum increase would follow a modified Fibonacci series in case of dose escalation (ie, 67%, 50%, 33%, etc.). Patients will be assigned to a dose that is closest to the current MTD prediction based on the mTPI method. The mTPI method relies upon a statistical probability algorithm, calculated using all patients treated in prior and current cohorts at the same dose level to determine (Decision Rules) where future cohorts should involve dose escalation, no change in dose, or dose de-escalation as presented in [Table 2](#).*

**Table 1. Dose Escalation Levels**

Dose Level	Dose (ng/kg)
1 (Starting Dose)	1.5
2	7.5
3	20
4	50
5	100
6	200
7	300
8	400

**Table 2. Decision Rules**

Number of Patients Having DLT	Number of Patient Treated at a Dose Level										
	n=2	n=3	n=4	n=5	n=6	n=7	n=8	n=9	n=10	n=11	n=12
0	E	E	E	E	E	E	E	E	E	E	E
1	S	S	S	S	E	E	E	E	E	E	E
2	U	D	S	S	S	S	S	S	E	E	E
3		U	U	D	D	S	S	S	S	S	S
4			U	U	U	D	D	D	S	S	S
5				U	U	U	U	D	D	D	D
6					U	U	U	U	U	U	U
7						U	U	U	U	U	U

D: De-escalate the dose; E: Escalate the dose; S: Stay at the dose; U: Unacceptable toxicity

Note: If one patient has a DLT event observed in a dose cohort with 1 patient enrolled, additional patients (eg, 1 or 2) may be enrolled for dose escalation assessment.

*Dose escalation will stop under any of the following conditions:*

- *The maximum sample size has been achieved;*
- *6-12 patients have been enrolled at a dose that is predicted to be the MTD;*
- *All doses explored appear to be overly toxic and the MTD cannot be determined.*

*Intrapatient dose escalation, other than the potential inclusion of a priming dose, will not be permitted in this study.*

#### 2.2.4. MTD Definition

*The estimated MTD is the dose level associated with approximately 27.5% of DLT-evaluable patients experiencing a DLT. The target interval for the DLT rate is (22.5%-32.5%). Due to the discreteness of the dose levels and in the interest of the safety of patients, the estimated MTD is the highest tested dose level with DLT rate  $\leq 0.325$  in at least 6-12 DLT evaluable patients for DLT. The study aims to determine a MTD for a dose regimen that does not include a priming dose administered IV, and an independent MTD for an IV dose regimen that includes a priming dose. In addition, the study aims to determine a MTD for PF-06671008 administered SC and may also determine an independent MTD for a SC dose regimen that includes a priming dose.*

#### 2.3. Dose Expansion Phase (Part 2)

*The maximum sample size for each tumor indication (ie, TNBC, CRC and NSCLC) will be in the range of n=10 to 20 evaluable patients. Enrollment of patients in one indication may be discontinued if minimal or no anti-tumor activity (eg, 0 or 1 response) is observed in the first 10 evaluable patients for that indication.*

### 2.3.1. Recommended Phase 2 Dose (RP2D) Definition

*The RP2D is the dose chosen for further study based on Phase 1 study results. If the MTD proves to be clinically feasible for long-term administration in a reasonable number of patients, then this dose usually becomes the RP2D. Further experience with the MTD may result in a RP2D dose lower than the MTD (eg, if in the expansion part >25% of patients require a dose reduction due to toxicity, then the sponsor and investigator determine if a lower RP2D needs to be determined).*

## 3. ENDPOINTS AND COVARIATES: DEFINITIONS AND CONVENTIONS

### 3.1. Primary Endpoint(s)

#### Primary Endpoint (Part 1)

- *First cycle Dose-Limiting Toxicities (DLTs).*

[figure not shown]
#### Primary Endpoint (Part 2)

- *Objective response (OR) as determined by the Response Evaluation Criteria in Solid Tumor (RECIST) version 1.1 criteria ([Appendix 3](#)).*

[figure not shown]
### 3.2. Secondary Endpoint (s)

- *Adverse Events as characterized by type, frequency, severity (as graded by National Cancer Institute Common Terminology Criteria for Adverse Events (NCI CTCAE) v.4.03) timing, seriousness, and relationship to study therapy;*
- *Laboratory abnormalities as characterized by type, frequency, severity (as graded by NCI CTCAE v.4.03) and timing;*
- *Vital sign abnormalities;*
- Pharmacokinetic parameters of PF-06671008 Single Dose (SD) -  $C_{max}$ ,  $T_{max}$ ,  $AUC_{sd,\tau}$ ,  $t_{1/2}$ ,  $AUC_{inf}$ , and CL for intravenous (IV) administration or apparent clearance (CL/F) for subcutaneous (SC) administration as data permit. Multiple Dose (MD) (assuming steady state is achieved) -  $C_{max,ss}$ ,  $T_{max,ss}$ ,  $AUC_{ss,\tau}$ ,  $t_{1/2}$ ,  $C_{min,ss}$ , CL for IV or CL/F for SC, volume of distribution ( $V_{ss}$ ) for IV or apparent volume of distribution at steady state ( $V_{ss}/F$ ) for SC, and  $R_{ac}$  ( $AUC_{ss,\tau}/AUC_{sd,\tau}$ ) as data permit;
- Incidence and titers of anti-drug antibodies (ADA) and neutralizing antibodies against PF-06671008;
- *Objective response, as assessed using the RECIST version 1.1 – Part 1 only;*
- *Progression Free Survival (PFS) and Overall Survival (OS) – Part 2 only.*

CCI

CCI

Covariates may also be considered when exploring QTc and PK relationship.

#### 4. ANALYSIS SETS

Several analysis sets are defined and will be considered for this study.

##### 4.1. Full Analysis Set

The full analysis set includes all enrolled patients. This is equivalent to the ITT (intent-to-treat) population.

##### 4.2. Safety Analysis Set

The safety analysis set includes all enrolled patients who receive at least one dose of study medication.

##### 4.3. 'PER PROTOCOL' Analysis Set (Part 1)

[figure not shown]
The per protocol analysis set includes all enrolled patients who receive at least one dose of study treatment and who do not have major treatment deviations during the first cycle. Patients with major treatment deviations during the first cycle of treatment are not evaluable for the MTD assessment and will be replaced as needed to permit MTD estimation. Major treatment deviations include failure to satisfy major entry criteria (eg, confirmation of the target disease; signed informed consent) or use of other anticancer treatments during the active treatment and disease follow-up phases other than as defined/allowed in this protocol.

#### 4.4. PK Analysis Set

*The PK parameter analysis population is defined as all enrolled patients treated who have sufficient information to estimate at least 1 of the PK parameters of interest and who have no major protocol deviations influencing the PK assessment.*

CCI

.

#### 4.6. Modified Intent-to-Treat Set

*The modified intent-to-treat (mITT) population is defined as all the randomized subjects who have received at least 1 dose of study medication, have measurable disease baseline assessment (within 28 days prior to study entry) and at least 1 post baseline assessment or disease progression or death before the first tumor assessment. The mITT population may be used for interim analysis and conference presentations when the study is still ongoing.*

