4.1. Inclusion Criteria

Patient eligibility should be reviewed and documented by an appropriate member of the investigator's study team before patients are included in the study.

Patients must meet all of the following inclusion criteria to be eligible for enrollment into the study:

1. For dose escalation (Part 1): Histological or cytological diagnosis of a tumor type with the potential to have P-cadherin expression (see [Appendix 2](#)). Patients with tumor types other than those listed in [Appendix 2](#) may be allowed to enroll based on emerging data and with the agreement of the sponsor. Patients must be refractory to, intolerant of established therapy known to provide clinical benefit for their condition, ie, patients must not be candidates for regimens known to provide clinical benefit.
2. For dose escalation (Part 1): Must have tumor tissue available for submission to the sponsor. Patients enrolled in Part 1 should have access to their archival formalin-fixed paraffin embedded material containing tumor that is of diagnostic quality and representative of their diagnosed malignancy or consent to undergo a biopsy during screening.
3. For dose expansion (Part 2): Histological or cytological diagnosis of previously treated CRC, TNBC or NSCLC with at least one measurable lesion, not previously irradiated, as defined by RECIST version 1.1 ([Appendix 4](#)). Patients must be refractory to, intolerant of established therapy known to provide clinical benefit for their condition, ie, patients must not be candidates for regimens known to provide clinical benefit.
4. For dose expansion (Part 2): Must have tumor tissue available for P-cadherin expression evaluation and must meet minimum required P-cadherin expression level (to be determined prior to activation of Part 2). Patients enrolled in Part 2 should have access to their archival formalin-fixed paraffin embedded material containing tumor that is of diagnostic quality and representative of their diagnosed malignancy.
5. For dose expansion (Part 2): Must have at least one tumor lesion, not previously irradiated, that is amenable to biopsy and must agree to undergo biopsies required per the [Schedule of Activities](#).

6. Age \geq 18 years.
7. Eastern Cooperative Oncology Group (ECOG) Performance Status (PS) must be 0 or 1.
8. Total body weight \geq 70 kg (154 lbs) for IV starting dose level only.
9. Adequate bone marrow function, including:

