9.1. Analysis Sets

Data analysis will be performed on the following analysis populations:

1. Safety analysis set.
 - The safety analysis set includes all enrolled patients who receive at least one dose of study treatment.
2. Full analysis set.
 - The full analysis set includes all enrolled patients.

3. Per-protocol analysis set (evaluable for MTD).

- The per protocol analysis set includes all enrolled patients who receive at least one dose of study treatment and who do not have major treatment deviations during first cycle. Patients with major treatment deviations during the first cycle of treatment are not evaluable for the MTD assessment and will be replaced as needed to permit MTD estimation. Major treatment deviations include failure to satisfy major entry criteria (eg, confirmation of the target disease; signed informed consent) or use of other anticancer treatments during the active treatment and disease follow-up phases other than as defined/allowed in this protocol.

[figure not shown]
4. Modified Intent-to-Treat (mITT) Population.

- The modified intent-to-treat (mITT) is the analysis population that will follow the ITT principle and include patients receiving at least 1 dose of study medication with baseline assessment and at least 1 post baseline assessment, disease progression, or death before the first tumor assessment. The mITT population may be used for interim analysis and conference presentations when the study is still ongoing.

5. PK analysis sets.

- The PK parameter analysis population is defined as all enrolled patients treated who have sufficient information to estimate at least 1 of the PK parameters of interest and who have no major protocol deviations influencing the PK assessment.

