## 1. VERSION HISTORY

This is the second version of the statistical analysis plan, based on the protocol dated Jan 12, 2018.

Texts taken directly from the protocol are made *Italicized*.

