#### **4. Recording Tumor Assessments**

All sites of disease must be assessed at baseline. Baseline assessments should be done as close as possible prior to study start. For an adequate baseline assessment, all required scans must be done within 28 days prior to treatment and all disease must be documented appropriately. If baseline assessment is inadequate, subsequent statuses generally should be indeterminate.

*Note: For the patient population being evaluated in this protocol, the baseline assessment may be completed within 6 weeks prior to randomization.*

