**Table 6. Objective Response Status at each Evaluation for Patients with Non Target Disease Only**

Non-target Disease	New Lesions	Objective status
CR	No	CR
Non-CR/Non-PD	No	Non-CR/Non-PD
Indeterminate	No	Indeterminate
Uequivocal progression	Yes or No	PD
Any	Yes	PD

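### SAP 4.6 adds three conditions to the protocol's mITT set, and the measurable-disease condition drops some treated Part 1 patients from the response and time-to-progression tables

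*SAP*

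**What the plan says.** **The two definitions.** Protocol 9.1 describes the mITT set as following the ITT principle and made up of "patients receiving at least 1 dose of study medication with baseline assessment and at least 1 post baseline assessment, disease progression, or death" (a death counts if no tumor assessment has yet been made). SAP 4.6 defines it as "all the randomized subjects who have received at least 1 dose of study medication, have measurable disease baseline assessment", adds in brackets that this assessment falls "within 28 days prior to study entry", and then asks for a post-baseline assessment, progression or early death, as the protocol does.

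**How the SAP labels its text.** SAP section 1 says "Texts taken directly from the protocol are made" italic. The paragraph in SAP 4.6 is italic.

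**Who is enrolled.** Protocol 4.1, criterion 1, opens "For dose escalation (Part 1): Histological or cytological diagnosis of a tumor type with the potential to have P-cadherin expression" and sets no measurability requirement. Criterion 3 asks for at least one measurable lesion, for Part 2 only. Under protocol 5.1 patients are allocated by sequential available slots.

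**Where the set is used.** SAP 6.3.1 runs the efficacy analysis in mITT and allows summaries for Part 1, Part 2 and both together. Its overview table assigns mITT to overall response, PFS, TTP, DOR and DOSD, and ITT to overall survival. SAP 3.2 lists Part 1 objective response as a secondary endpoint, and PFS as a Part 2 endpoint only.

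**What else the SAP provides.** Table 6 in SAP Appendix 3 is titled "Objective Response Status at each Evaluation for Patients with Non Target Disease Only". The same appendix, like protocol Appendix 4, notes that "the baseline assessment may be completed within 6 weeks prior to randomization".

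**The concern.** A programmer who sees italic text in SAP 4.6 will take it as the protocol's definition and build the set from it. The result is narrower than the protocol's set, and nothing in the SAP declares or justifies the change.

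The measurable-disease condition matters most. Part 1 may enrol patients who have only non-target disease. The SAP has a table for scoring them, then leaves them out of the population in which response is tabulated. Some restriction may be arguable for a response rate, since these patients cannot reach a partial response. It is harder to defend for time to progression, because Table 6 lets them progress.

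At stake are the denominator of a Part 1 secondary endpoint, the pooled Part 1 and Part 2 tables, and agreement between protocol and SAP on the main efficacy set.

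**Working it through.** **Step 1. Compare the conditions.**

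| Condition | Protocol 9.1 | SAP 4.6 | Rest of the documents |
|---|---|---|---|
| Entry | at least one dose | randomised, at least one dose | no randomisation (protocol 5.1) |
| Baseline disease | a baseline assessment | measurable disease at baseline | required in Part 2 only (protocol 4.1) |
| Baseline window | none stated | 28 days before study entry | 6 weeks = 42 days allowed (protocol Appendix 4, SAP Appendix 3) |
| After baseline | assessment, progression or early death | the same | no conflict |

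The first row is a wording error. The second removes patients. The third could remove a patient scanned 29 to 42 days before entry, in either part.

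**Step 2. Who leaves which table.** A treated patient without measurable disease has only non-target disease. SAP Table 6 gives that patient CR, Non-CR/Non-PD, Indeterminate or PD.

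- Response: the patient leaves the Part 1 and pooled denominators.
- TTP: the patient could progress or be censored, but leaves the table. The TTP row of SAP 6.3.1 is not restricted to Part 2.
- PFS: the patient is lost only if PFS is tabulated for Part 1 or pooled.
- DOR: only a patient with CR could have contributed.
- DOSD: Table 6 never returns a stable status, so no loss is shown.
- Part 2: every eligible patient has a measurable lesion, so this condition removes nobody.

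**Step 3. Direction of the effect on response.** Let N be the patients in the protocol's set, x the responders, m the patients excluded for non-measurable disease, and c the CRs among those m.

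- Protocol rate: x/N. SAP rate: (x - c)/(N - m).
- The SAP rate is higher when N(x - c) > x(N - m), that is, when c/m < x/N.
- If c = 0 and x > 0, the ratio of the two rates is N/(N - m) = 1/(1 - share excluded).

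**Step 4. Size, for illustration.** The documents give no share and no responder count. I take N = 92, the approximate maximum enrolment for Part 1 (SAP 5.2.1), as an upper bound on the mITT count. I assume x = 8 and shares of 10%, 15% and 25%. Intervals are exact 95% (SAP 5.3.2), with c = 0.

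| Share excluded | m | Response rate | Exact 95% CI | 1/(1 - share) |
|---|---|---|---|---|
| none | 0 | 8/92 = 8.7% | 3.8 to 16.4% | 1.00 |
| 10% | 9 | 8/83 = 9.6% | 4.3 to 18.1% | 1.11 |
| 15% | 14 | 8/78 = 10.3% | 4.5 to 19.2% | 1.18 |
| 25% | 23 | 8/69 = 11.6% | 5.1 to 21.6% | 1.33 |

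The shift is 0.9 to 2.9 percentage points, small against the width of the intervals.

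**Step 5. When the direction changes.** With 9 excluded and one CR among them, c/m = 1/9 = 11.1%, above 8.7%, and the SAP rate falls to 7/83 = 8.4%. With 23 excluded and two CRs, c/m = 2/23 = 8.7% and the rates are equal: 6/69 = 8/92. With no responders both rates are 0%.

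**The case against.** The other side has several good points.

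- **The SAP may depart from the protocol.** SAP section 2 says so, and asks for an amendment only for major changes to the primary endpoint or its analysis. This stands. But a departure should be visible as one, and this one is printed as protocol text.
- **A measurable-disease denominator for response is defensible.** This also stands, for response alone. It does not carry over to TTP, and the SAP applies the one set to both.
- **The patients are not lost from the report.** SAP 5.4.2 and protocol 9.4 list tumor response by patient without an mITT restriction. So the exclusion concerns the summary tables, not all reporting of their response.
- **The protocol does not itself prescribe an mITT response rate for Part 1.** It says the set may be used for interim analysis and conference presentations. So the comparison is between two definitions of one set, not between two prespecified results.
- **No analyst would produce an empty set.** Agreed. References to randomisation recur loosely in both documents, and this one needs only correcting.
- **The 28-day window has support.** The Schedule of Activities puts screening within 28 days before registration, and both RECIST appendices state 28 days before adding the 6-week note. The number affected may be small, but the conflict remains.

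A reader might also infer more than the documents support:

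- that the response rate must rise; it need not, because CR remains possible;
- that the planned PFS endpoint loses patients; it is a Part 2 endpoint, and Part 2 requires a measurable lesion;
- that duration of stable disease loses the same share; non-target-only patients are never classed as stable in Table 6.

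**Conclusion.** The conflict holds as a matter of text. SAP 4.6 is marked as protocol wording but adds randomisation, measurable disease and a 28-day window to protocol 9.1. Applied through SAP 6.3.1, it drops treated Part 1 patients with non-target disease only from the Part 1 and pooled response and TTP tables, and from PFS if that is tabulated outside Part 2.

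The effect on the Part 1 response rate is probably upward and modest: about 1.11 times at 10% excluded and 1.33 times at 25%, provided that some patients respond and none of those excluded does. The shares are assumptions, as are the 8 responders behind the percentages. The direction for TTP or PFS cannot be stated. The Part 2 primary endpoint is not affected by the measurable-disease condition; the 28-day window could touch Part 2 patients, by an amount the documents do not let one size.

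This is a minor point: a secondary endpoint, no hypothesis tests (SAP 5.1), and an inexpensive correction.

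**What to change.** In SAP 4.6:

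1. Replace *randomized* with *enrolled*.
2. Delete the measurable-disease condition.
3. Remove the 28-day window, or reconcile it with the 6-week allowance in protocol Appendix 4 and SAP Appendix 3. The first two edits alone would still leave the set different from protocol 9.1.

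In SAP 6.3.1, use this corrected mITT set for Part 1 and pooled response, TTP and any PFS tables outside Part 2. Report response among patients with measurable disease as a labelled supportive row, so that readers see both denominators.

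The cost is SAP wording and one extra table row, with no new data. If the window is reconciled by changing the appendix note instead of SAP 4.6, protocol Appendix 4 must change too. The downside is that the Part 1 response rate may look slightly less favourable.

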#### 4.7. Immunogenicity Analysis Set

*The immunogenicity analysis set is defined as patients who receive at least 1 dose of study treatment and have at least 1 ADA sample analyzed.*

#### 4.8. Protocol Deviations

The determination of protocol deviations (PDs) and important protocol deviations (IPDs) will follow Pfizer standard operating procedures. A full list of PDs, IPDs, and IPDs that exclude a patient from the Per-protocol analysis will be determined prior to the database release and be included in the CSR.

